5.2 OTHER ENDPOINTS

Not Applicable

5.3 COVARIATES

Not Applicable

6 HANDLING OF MISSING VALUES

No imputation for missing values will be performed.

7 STATISTICAL METHODOLOGY AND STATISTICAL ANALYSES**7.1 STATISTICAL METHODS**

Analysis of the data will be performed by the Biostatistics and Statistical Programming team. All statistical analyses will be performed using STATA 13.0 Version or higher. The SAP will be finalized before database lock.

The following standard descriptive summaries will be presented:

[figure not shown]
[figure not shown]
Descriptive statistics for continuous data:

The continuous data will be summarized using the number of observations (n), arithmetic mean (mean), standard deviation (SD), median, minimum value (min), and maximum value (max).

The number of observations (n) will be presented with no decimal place, mean and median will be presented up to one decimal place from the original value, SD up to two decimal places from the original value and (min, max) as an original value.

Descriptive statistics for categorical data:

PFIZER CONFIDENTIAL

The categorical variables will be summarized using the frequency count (n) and percentage (%) for each possible value. The frequencies will be presented up to 0 decimal places, percentage up to 1 decimal place.

All the analysed variable will be presented by the line of treatment (1st line of treatment and 2nd and later line). If data are not available, a missing category will be presented. Statistical tests, if any, will be performed at 5% level of significance. The denominator for percentages will be based on the number of patients appropriate for the purpose of the analysis.

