## 8. RESEARCH QUESTION AND OBJECTIVES

The primary objective of this real-world study is to describe patient demographics, clinical characteristics, treatment patterns and clinical outcomes of adult female patients who have received palbociclib combination treatments for HR+/HER2- ABC/MBC in real world settings in India:

- Palbociclib in combination with aromatase inhibitor (as prescribed by the Physician) for the treatment of postmenopausal women with HR+/HER2- advanced breast cancer as initial endocrine-based therapy for their metastatic disease.
- Palbociclib for the treatment of hormone receptor HR+/HER2- advanced or metastatic breast cancer in combination with fulvestrant in women with disease progression following endocrine therapy.

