### Primary objectives

- To describe the demographics and clinical characteristics of patients who have received palbociclib combination with aromatase inhibitor (as prescribed by the Physician) in menopausal state as initial endocrine therapy in MBC or with fulvestrant after progression on prior endocrine therapy.
- To summarize adjuvant therapies received for the treatment of early or locally advanced breast cancer (Stages 0-IIIa).
- To describe treatments received in the advanced/metastatic setting, before and after palbociclib combination use.
- To describe dosing and dose changes, interruptions, delays, and discontinuations associated with palbociclib use in clinical practice.
- To describe supportive therapies received by patients while receiving palbociclib combination treatments.
- To determine in overall population and defined subgroups, clinical outcomes including (but not limited to):
  - Proportion of patients who are progression free at specific intervals (eg, 6, 12, 18 months).
  - Objective response rate (ORR) - depending on availability of follow-up data.
  - Proportion of alive patients 1 and 2 years post palbociclib combination initiation - depending on availability of follow-up data (sample size permitting).

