#### Patient inclusion criteria

Patients must meet all of the following inclusion criteria to be eligible for inclusion in the study:

- $\geq 18$  years old females.
- HR+/HER2- breast cancer diagnosis with confirmed metastatic or advanced disease.
- Received palbociclib with aromatase inhibitor (as prescribed by the Physician) as initial endocrine therapy in postmenopausal MBC patients or with fulvestrant in patients who have progressed on prior endocrine therapy

- Patients on LHRH agonists for ovarian function suppression in pre- or perimenopausal stage only if prescribed palbociclib with fulvestrant.
- No prior or current enrolment in an interventional clinical trial for ABC/MBC.
- Minimum of 3 months of follow up data since palbociclib with fulvestrant initiation, or minimum of 6 months of follow up data since palbociclib with aromatase inhibitor initiation.

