### 9.3 Variables

**Table 1. List of Study Variables**

Variable	Role	Data Source(s)	Operational Definition
Patient demographics	Baseline Sub-group identifier	Patient records	Age, ethnicity, weight, height, biomarker status, family history of breast cancer.
Clinical characteristics	Baseline Sub-group identifier	Patient records	Time since diagnosis, staging, node status, menopause status. ECOG/Karnofsky functional status, diagnosis for which palbociclib combination was prescribed, sites of metastases, de novo vs. recurrent disease.
Comorbid conditions	Baseline Sub-group identifier	Patient records	Comorbid conditions.
Early treatment history	Baseline Sub-group identifier	Patient records	Adjuvant treatments received since breast cancer diagnosis, time since end of adjuvant treatment, surgery/radiotherapy received.
Advanced treatment history	Baseline Sub-group identifier	Patient records	Treatments and supportive therapies received since metastatic/advanced HR+/HER2- diagnosis, duration of treatments, reasons for regimen changes.
Palbociclib combination treatment	Exposure Sub-group identifier	Patient records	Starting dose, duration of treatment, line of treatment, changes in dose, interruptions, cycle delays and discontinuations; where possible reasons for change in treatment.
Clinical outcomes	Outcomes	Patient records	Proportion progression free, ORR, TTP, PFS, patient death, 1-year and 2-year survival in all patients and within specific subgroups.

PFIZER CONFIDENTIAL

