- Received palbociclib with aromatase inhibitor (as prescribed by the Physician) as initial endocrine therapy in postmenopausal MBC patients or with fulvestrant in patients who have progressed on prior endocrine therapy.
- Patients on LHRH agonists for ovarian function suppression in pre- or perimenopausal stage only if prescribed palbociclib with fulvestrant.
- No prior or current enrolment in an interventional clinical trial for ABC/MBC.
- Minimum of 3 months of follow up data since palbociclib with fulvestrant initiation, or minimum of 6 months of follow up data since palbociclib with aromatase inhibitor initiation

Exclusion criteria

[figure not shown]
[figure not shown]
Patients meeting any of the following criteria will not be included in the study:

- Cancers other than breast cancer
- Male breast cancer
- Indications other than mentioned in the protocol
- Visceral crisis

Treatment/cohort labels

Palbociclib

PFIZER CONFIDENTIAL

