4.4 SUBGROUPS

Not Applicable

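### The SAP defines no subgroups and splits its visible tables only by line of treatment, a partial proxy for the two regimens (aromatase inhibitor or fulvestrant) on which the study is built

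*SAP*

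**What the plan says.** **Objective.** The sixth primary objective, worded alike in Protocol section 8 and SAP 2.2, reads: "To determine in overall population and defined subgroups, clinical outcomes including (but not limited to". Protocol Table 1 repeats the intention for outcomes, ending with "1-year and 2-year survival in all patients and within specific subgroups", and gives six of its seven variable rows the role of sub-group identifier.

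**Regimens.** Protocol section 8 sets out two indications. The aromatase inhibitor is given "as initial endocrine-based therapy for their metastatic disease". The other is palbociclib "in combination with fulvestrant in women with disease progression following endocrine therapy". Both documents set follow-up by regimen; SAP 2.1 has "Minimum of 3 months of follow up data since palbociclib with fulvestrant initiation, or minimum of 6 months of follow up data" for the aromatase inhibitor. Protocol 9.1 lets the index date differ by combination partner.

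**Analysis.** The SAP section headed "4.4 SUBGROUPS" contains only the entry Not Applicable. SAP 7.1 then says: "All the analysed variable will be presented by the line of treatment (1st line of treatment and 2nd and later line". SAP 2.1 has one cohort label, Palbociclib. The list of tables (SAP section 8) has Tables 1 to 11, each with one companion table by line. The visible shells in Appendix 1 have a single Palbociclib column.

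**The concern.** An objective that calls for subgroup outcomes needs an SAP that says which subgroups. SAP 4.4 names none, and it also disagrees with SAP 7.1, which does apply a subgroup split, by line.

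Combination partner is the evident candidate left out. Indication, index date, minimum follow-up and menopausal eligibility all depend on it (Protocol 8, 9.1 and 9.2.1), yet no visible table reports which partner a patient received or gives any result by partner. If the regimens are mixed within a line, a reader of the by-line response, dose-change or outcome tables cannot tell which regimen the figures describe, or how far a difference between lines reflects a difference in regimen mix.

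**Working it through.** **1. The plan's own study size.** Protocol Table 2 adds up:
- physicians: 1+1+2+2+1+1+1+1 = 10
- records: 20+10+40+20+10+10+20+20 = 150

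The 7:3 ratio of first to later line (Protocol 9.1) gives 0.7 × 150 = 105 and 0.3 × 150 = 45. No ratio of aromatase inhibitor to fulvestrant is given. The study is descriptive, so there is no power figure to reproduce.

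**2. Does line identify partner?** Protocol 9.1 counts line within metastatic disease. The eligibility criteria in Protocol 9.2.1 leave both off-diagonal cells open.

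| | Aromatase inhibitor | Fulvestrant |
|---|---|---|
| First line | Expected | Possible: the required progression on endocrine therapy is not tied to the metastatic setting, so it may have occurred on adjuvant therapy |
| Later line | Possible: initial endocrine therapy may follow chemotherapy for metastatic disease | Expected |

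**3. Is partner shown anywhere?** In the visible shells, Table 10 gives line. Table 8 asks only whether partner therapy was continued. Table 11 gives response categories, ORR and CBR. None names the partner.

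**4. Illustration of mixing.** Inputs are the median progression-free survival times in Protocol section 7: 24.8 months with letrozole and 9.5 months with fulvestrant. Assume exponential times, S(t) = 0.5^(t/median), and apply the 9.5-month median to all fulvestrant patients.
- Aromatase inhibitor, 12 months: 0.5^(12/24.8) = 71.5%
- Fulvestrant, 12 months: 0.5^(12/9.5) = 41.7%

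With a share s of first-line patients on fulvestrant, the first-line figure is (1 − s) × 71.5% + s × 41.7%:

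| s (assumed) | First-line 12-month share |
|---|---|
| 0% | 71.5% |
| 10% | 68.5% |
| 30% | 62.6% |
| 50% | 56.6% |

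The shift from no mixing is therefore 0 to about 15 points (71.5 − 56.6 = 14.9).

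**5. Precision of a by-partner table.** The 95% half-width is 1.96 × √(p(1 − p)/n), taken at p = 0.5. Assume partner splits 7:3, as line does:
- all patients, n = 150: ±8.0 points
- aromatase inhibitor, n = 105: ±9.6 points
- fulvestrant, n = 45: ±14.6 points

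**The case against.** **Partner is not a named subgroup.** A reader might infer that the protocol defines partner as a subgroup and the SAP drops it. The visible text does not support that. In Protocol Table 1 the row for palbociclib combination treatment lists line but not partner, and the only patient mix the protocol sets is by line. SAP 7.1 therefore delivers a split on a variable the protocol does name. This stands: the case for partner is an inference from how the study is built.

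**Line already captures much of the difference.** This stands in part. A reader might compare the two pure regimens and conclude that gaps of 20 to 34 points are hidden (84.6% against 64.5% at 6 months, 60.5% against 26.9% at 18 months, same assumptions). That ignores the by-line tables; the relevant quantity is residual mixing within a line. The two medians also come from trials in different populations, so the gap combines partner with prior-treatment setting. And no visible table reports progression-free proportions, so the figures show scale and do not measure error in a planned table.

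**Redaction.** Text is blacked out in Protocol 9.7, in SAP 7.2, within Table 11 and after Table 11.1. A regimen breakdown there cannot be excluded, so it would be too strong to say that no table separates the regimens. However, the list of tables shows no redaction and ends at Table 11.1 without a by-partner entry, and SAP 4.4 is fully legible.

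**Collection of partner.** The CRF is not among the documents. Eligibility and the follow-up minimum cannot be checked without knowing the partner, so its availability is likely but not documented.

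**Conclusion.** The concern holds in this form: both documents ask for outcomes in defined subgroups, SAP 4.4 defines none, and the only visible split, by line, is an incomplete proxy for the two regimens. The by-line tables can mix regimens, and no visible table lets a reader see how much.

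The size cannot be fixed from the documents, because the partner mix within each line is not given. The 0 to 15 point range for first-line 12-month progression-free share rests on the protocol's background medians, exponential times and an assumed 0% to 50% fulvestrant share. It is an illustration only.

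A linked inconsistency needs settling with it. SAP 4.1 describes the 150 patients, and SAP 5.1 the endpoint, as aromatase-inhibitor only, while the SAP's own inclusion criteria admit fulvestrant patients. A reader might take this as a decision to exclude the fulvestrant group. The objectives and criteria do not support that, but the sections must be made consistent before any by-partner table has a clear denominator.

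**What to change.** 1. In SAP 4.4, replace Not Applicable with two subgroups: line of treatment (first; second and later) and combination partner (aromatase inhibitor; fulvestrant).
2. Add by-partner versions of the tables, Table 11 outcomes first. Keep the overall and by-line tables.
3. Report the partner-by-line counts, so that the mixing within each line is visible. Full outcome tables crossed by both factors are not needed; with about 45 later-line patients the cells would be sparse.
4. Reword SAP 4.1 and 5.1 so that fulvestrant patients are in the analysis set and covered by the endpoint, in line with SAP 2.1 and 2.2.
5. Confirm that the CRF records partner for every patient.

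The cost is SAP wording and extra tabulation, with no new patients and no testing. The downside is imprecision: about 45 fulvestrant patients under the assumed 7:3 split, with a 95% half-width near 15 points at p = 0.5. By-partner results should therefore carry their denominators and intervals and be read as description.

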7.2 STATISTICAL ANALYSES

- **Demographic Characteristics**

The demographic and baseline characteristics will be summarized by using descriptive statistics. Continuous variables such as age will be summarized by number of observations (n), arithmetic mean (mean), standard deviation (SD), median, minimum value (min), and maximum value (max) and Categorical variables such as menopausal status, induced menopause, family history of breast cancer and patient deceased will be presented by frequency (n) and percentage (%).

- **Initial and advance breast cancer diagnosis**

For all the patients initial diagnosis of breast cancer stages (stage 0 to stage IV) will be presented in frequency counts (n) and percentage (%). For the advance stages (stage IIIb, IIIc or IV) of breast cancer patients again locoregionally advanced or metastatic frequency counts (n) and percentage (%) will be given. For the metastatic disease, sites of metastases such as Bone, Liver, Brain, Lung, Lymph nodes and others with further segregation like single or multiple locations will be presented in frequency (n) and percentage (%).

- **Prior Therapy**

For all patient's prior therapy type (Targeted, Endocrine and Chemotherapy) will be presented by frequency count and percentage

- **Performance status**

Performance status using ECOG scale at the initiation of palbociclib treatment. Status is measured using 4 point scale from fully active to completely disable and will be summarized by frequency (n) and percentage (%).

- **Early Breast Cancer Treatment History**

Following early breast cancer diagnosis treatments received such as surgery, radiotherapy, neoadjuvant treatment, adjuvant chemotherapy, adjuvant endocrine therapy by patients will be summarized by frequency (n) and percentage (%).

- **Palbociclib Treatment**

PFIZER CONFIDENTIAL

For all the patients initial dose prescribed of palbociclib, any dose adjustments made to palbociclib and for each dose adjustment if dose reduced or increased, palbociclib was temporarily interrupted, cycle delay and reason for dose change will be summarized by frequency (n) and percentage (%). Moreover, complete summary (frequency and percentage) of all supportive therapies that patients received will be presented.

- **Advance Breast Cancer Treatment History**

For all the patients' line of treatment for Palbociclib combination started will be given in frequency and percentage, time (months) from diagnosis of breast cancer to start of Palbociclib combination will be presented as mean, median, standard deviation and range value (minimum and maximum). **CCI**

CCI

[figure not shown]
- **Clinical Outcome**

For all the patients initially recorded responses like complete positive response to the disease, partial positive response to the disease, stable disease and progressive disease, will be summarized with frequency counts (n) and percentages (%). Moreover, based on initial response, objective response rate (ORR) and clinical benefit rate (CBR) will be calculated and presented as percentage.

CCI

PFIZER CONFIDENTIAL

PFIZER CONFIDENTIAL

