## 9. RESEARCH METHODS

### 9.1 Study Design

This is a post marketing, retrospective, non-interventional study (NIS). The study will be conducted as a retrospective medical record review of patients who have received palbociclib combination with aromatase inhibitor (as prescribed by the Physician) in menopausal state as initial endocrine therapy in MBC or with fulvestrant after progression on prior endocrine therapy. It will comprise of an initial screening and eligibility assessment of patients followed by data collection from eligible patient records.

Data collection will be conducted using a predesigned electronic case report form (eCRF). Eligible physicians will be invited to complete the eCRF of patients that meet the study criteria. Each eCRF will take around 25 minutes to complete. Patient eligibility will be confirmed by treating physicians. In order to allow for a sufficiently long observational window, treating physicians will be asked to go back to a specific point in time, the index date, and sequentially select the medical records of the next 'n' patients who meet the inclusion criteria. The 'index date' will be defined as 60 days after the physician first prescribed palbociclib + partner therapy following the availability of specific indication in the market (eg, if palbociclib + aromatase inhibitor was available on 25 October 2016 in India and the physician initiated a patient on palbociclib with aromatase inhibitor the next day, the index date will be 26 December 2016). The index date will differ for the specific indications/combination partners if approved on different dates.

The proportion of patients treated in accordance with the first line versus second or later line setting for metastatic disease will be approximately 7:3, as has been observed in the real world practice.

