2.2 STUDY OBJECTIVES

Primary Objectives:

1. To describe the demographics and clinical characteristics of patients who have received palbociclib combination with aromatase inhibitor (as prescribed by the Physician) in menopausal state as initial endocrine therapy in MBC or with fulvestrant after progression on prior endocrine therapy.
2. To summarize adjuvant therapies received for the treatment of early or locally advanced breast cancer (Stages 0-IIIa).
3. To describe treatments received in the advanced/metastatic setting, before and after palbociclib combination use.
4. To describe dosing and dose changes, interruptions, delays, and discontinuations associated with palbociclib use in clinical practice.
5. To describe supportive therapies received by patients while receiving palbociclib combination treatments.
6. To determine in overall population and defined subgroups, clinical outcomes including (but not limited to):
 - Proportion of patients who are progression free at specific intervals (eg, 6, 12, 18 months).
 - Objective response rate (ORR) - depending on availability of follow-up data.
 - Proportion of alive patients 1 and 2 years post palbociclib combination initiation -depending on availability of follow-up data (sample size permitting).

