8 LIST OF TABLES

Table 1 Demographic Characteristics – All Subjects

Table 1.1 Demographic Characteristics by line of treatment (1st line vs. 2nd and later line) – All Subjects

Table 2 Initial and Advance Breast Cancer Diagnosis – All Subjects

Table 2.1 Initial and Advance Breast Cancer Diagnosis by line of treatment (1st line vs. 2nd and later line) – All Subjects

Table 3 Advance Breast Cancer Diagnosis – All Subjects

Table 3.1 Advance Breast Cancer Diagnosis by line of treatment (1st line vs. 2nd and later line) – All Subjects

Table 4 Prior Therapy – All Subjects

Table 4.1 Prior Therapy by line of treatment (1st line vs. 2nd and later line) – All Subjects

Table 5 Performance Status – All Subjects

Table 5.1 Performance Status by line of treatment (1st line vs. 2nd and later line) – All Subjects

Table 6 Early Breast Cancer Treatment History – All Subjects

Table 6.1 Early Breast Cancer Treatment History by line of treatment (1st line vs. 2nd and later line) – All Subjects

Table 7 Palbociclib Treatment – All Subjects

Table 7.1 Palbociclib Treatment by line of treatment (1st line vs. 2nd and later line) – All Subjects

Table 8 Dose Adjustment – All Subjects

Table 8.1 Dose Adjustment by line of treatment (1st line vs. 2nd and later line) – All Subjects

Table 9 Palbociclib Treatment- Supportive Therapies – All Subjects

Table 9.1 Palbociclib Treatment- Supportive Therapies by line of treatment (1st line vs. 2nd and later line) – All Subjects

Table 10 Advance Breast Cancer Treatment History – All Subjects

Table 10.1 Advance Breast Cancer Treatment History by line of treatment (1st line vs. 2nd and later line) – All Subjects

Table 11 Clinical Outcome – All Subjects

Table 11.1 Clinical Outcome by line of treatment (1st line vs. 2nd and later line) – All Subjects

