10 APPENDICES

10.1 APPENDIX 1: MOCK SHELLS FOR TABLES

Table 1 Demographic Characteristics – All Subjects

Characteristic (Unit)	Statistics	Palbociclib (N=xx)
Age of the patients	n	xx
	Mean (SD)	xx.x (xx.xx)
	Median	xx.x
	Min, Max	xx, xx
Age group >65 yrs vs <65 yrs	n (%)	
Menopause Status		
Induced	n (%)	xx (xx.x)
Natural	n (%)	xx (xx.x)
Type of Induced Menopause		
LHRH suppression	n (%)	xx (xx.x)
Radioablation	n (%)	xx (xx.x)
Surgical	n (%)	xx (xx.x)
Patient deceased		
No	n (%)	xx (xx.x)
Yes	n (%)	xx (xx.x)
Family History of Breast Cancer		
No	n (%)	xx (xx.x)
Yes	n (%)	xx (xx.x)
Abbreviations: N = number of subjects in Palbociclib group; n = number of subjects in specified category; LHRH = Luteinizing Hormone Releasing Hormone		
Note 1: Percentages are based on the number of subjects in the Palbociclib group.		
Table 1.1 Demographic Characteristics by line of treatment (first line vs. second and later line)		

PFIZER CONFIDENTIAL

Table 2 Initial and Advance Breast Cancer Diagnosis– All Subjects

Characteristic (Unit)	Statistics	Palbociclib (N=xx)
Stage of Breast Cancer at diagnosis		
Stage I	n (%)	xx (xx.x)
Stage II	n (%)	xx (xx.x)
Stage IIIa	n (%)	xx (xx.x)
Stage IIIb	n (%)	xx (xx.x)
Stage IIIc	n (%)	xx (xx.x)
Stage IV	n (%)	xx (xx.x)
Type of breast cancer (Metastatic/ locally advanced)		
Locoregionally advanced	n (%)	xx (xx.x)
Metastatic	n (%)	xx (xx.x)
Abbreviations: N = number of subjects in Palbociclib group; n = number of subjects in specified category		
Note 1: Percentages are based on the number of subjects in the Palbociclib group.		
Table 2.1 Initial and Advance Breast Cancer Diagnosis by line of treatment (first line vs. second and later line)		

Table 3 Advance Breast Cancer Diagnosis – All Subjects

PFIZER CONFIDENTIAL

Characteristic (Unit)	Statistics	Palbociclib (N=xx)
Sites of Metastases		
Bone	n (%)	xx (xx.x)
Lung	n (%)	xx (xx.x)
Liver	n (%)	xx (xx.x)
Lymph nodes	n (%)	xx (xx.x)
-----	-----	-----
-----	-----	-----
Bone		
Single site	n (%)	xx (xx.x)
Multiple sites	n (%)	xx (xx.x)
Liver		
Single site	n (%)	xx (xx.x)
Multiple sites	n (%)	xx (xx.x)
Lung		
Single lung	n (%)	xx (xx.x)
Bilateral	n (%)	xx (xx.x)
Pleural effusion	n (%)	xx (xx.x)
Lymph Nodes		
Regional	n (%)	xx (xx.x)
Distal	n (%)	xx (xx.x)

Abbreviations: N = number of subjects in Palbociclib group; n = number of subjects in specified category

Note 1: Percentages are based on the number of subjects in the Palbociclib group.

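### Deaths are tabulated as a demographic percentage with no time horizon, overall and by line, although follow-up is unequal by design and the objective is survival at 1 and 2 years

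*SAP*

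**What the plan says.** **SAP, death as a descriptor.** Under Demographic Characteristics, SAP 7.2 says that categorical variables such as "menopausal status, induced menopause, family history of breast cancer and patient deceased will be presented by frequency (n) and percentage". In the Appendix 1 shell for Table 1, the row "Patient deceased" (No/Yes) stands between type of induced menopause and family history. The footnote sets the denominator: "Note 1: Percentages are based on the number of subjects in the Palbociclib group". Table 1.1 repeats the table for first line against second and later line, in keeping with the general rule in SAP 7.1. No time point, follow-up duration or censoring rule is attached to the row.

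**Objective and protocol method.** Objective 6 (SAP 2.2, protocol 8) includes "Proportion of alive patients 1 and 2 years post palbociclib combination initiation", subject to available follow-up and sample size. Protocol Table 1 places "patient death, 1-year and 2-year survival in all patients and within specific subgroups" in the row whose role is Outcomes. Protocol 9.7 plans Kaplan-Meier charts with 1-year and 2-year rates for time-to-event data.

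**Follow-up.** Protocol 9.1 sets the index date 60 days after each physician's own first prescription of the combination, and adds: "The index date will differ for the specific indications/combination partners if approved on different dates". Protocol 7 gives Indian approval as August 2016 with letrozole and December 2017 with fulvestrant. Minimum follow-up is 6 months for the aromatase inhibitor and 3 months for fulvestrant.

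**The concern.** Death after palbociclib start is an outcome whose frequency grows with time observed. A percentage deceased at the date the record was read mixes the death rate with the length of follow-up, and it cannot be converted into survival at 1 or 2 years.

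The by-line version in Table 1.1 is the more exposed use. If first-line women have been observed longer on average, they will show more deaths at the same risk. A real disadvantage in later lines would then look smaller than it is, or disappear. A reader of the report would take the two percentages as a mortality comparison, because nothing in the shell says otherwise.

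**Working it through.** The documents state no survival rate, event count or power figure, so there is no design figure to reproduce. The check has two parts: how unequal the windows can be, and what that does to a crude percentage.

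**1. Windows**
- Aromatase inhibitor: the worked example in protocol 9.1 gives an index date of 26 December 2016. (26 October 2016 plus 60 days is 25 December; the one-day difference is immaterial here.)
- Fulvestrant: 1 to 31 December 2017 plus 60 days gives 30 January to 1 March 2018.
- The earliest possible starts are therefore 13.1 to 14.1 months apart.
- Longest possible window at 30 November 2020 (collection was planned for November 2020 to January 2021): 47.1 months for the aromatase inhibitor and 33.0 to 34.0 months for fulvestrant.
- Required minimum: 6 and 3 months.

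**2. Model (assumed)**

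Both combinations have the same constant death rate λ = −ln(S24)/24 per month, where S24 is 2-year survival. Observation time is uniform between a (minimum) and b (maximum). The expected percentage deceased is

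100 × {1 − [exp(−λa) − exp(−λb)] / [λ(b − a)]}.

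For S24 = 70%, λ = 0.3567/24 = 0.01486.
- Aromatase inhibitor, 6 to 47.1 months: 1 − (0.9147 − 0.4966)/(0.01486 × 41.1) = 31.6%.
- Fulvestrant, 3 to 33.0 months: 1 − (0.9564 − 0.6124)/(0.01486 × 30.0) = 22.8%.

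**3. By line**

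If p is the aromatase inhibitor share in first line and q the share in later lines, the by-line gap is (p − q) × the gap by combination. The shares are assumed; the documents give none. Gaps are taken before rounding.

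| Assumed S24 | Aromatase inhibitor | Fulvestrant | Gap by combination | Gap by line, 90%/10% | Gap by line, 70%/30% |
|---|---|---|---|---|---|
| 60% | 41.3% | 30.7% | 10.7 | 8.5 | 4.3 |
| 70% | 31.6% | 22.8% | 8.7 | 7.0 | 3.5 |
| 80% | 21.4% | 15.1% | 6.3 | 5.0 | 2.5 |

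The true difference is zero in every row.

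**4. Sensitivity**
- A fulvestrant maximum of 34.0 months gives 5.9 to 10.0 points by combination.
- Six more months on both maxima (53.1 and 39.0), in case collection ran later, gives 6.1 to 10.0 points. The SAP cites a CRF dated 20 May 2021.

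**5. What it can mask**

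At S24 = 70%, crude percentages are equal by line when the later-line death rate is truly higher by a factor of about 1.5 (complete overlap of line and combination), 1.37 (90%/10%) or 1.17 (70%/30%). For example, at 90%/10% with a factor of 1.3, first line shows 30.7% deceased and later lines 29.4%.

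**6. At a fixed horizon**

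With S24 = 70% in both groups, the expected percentage dead is 30% at 24 months and 1 − √0.70 = 16.3% at 12 months in each. Kaplan-Meier at those times removes this artefact, provided censoring is unrelated to prognosis.

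**The case against.** **The survival analysis may be in the SAP, blacked out.** This stands. Redactions follow the Clinical Outcome text in SAP 7.2 and cover parts of Tables 11 and 11.1. The visible methods in SAP 7.1 list only continuous and categorical summaries, but figures are missing there too. A reader might infer that the SAP drops the 1- and 2-year survival analysis; the documents do not support that. Nothing hidden, however, changes the visible rows in Tables 1 and 1.1.

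**A plain death count is legitimate.** Partly right. The protocol abstract describes demographics at the time of data collection, which fits vital status at record review, and protocol Table 1 lists patient death separately from 1- and 2-year survival. The SAP nowhere says that this row answers objective 6. A count is fine; a percentage by line without follow-up time is not.

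**The difference in windows is inferred.** This stands. It would be tempting to say that observation windows differ by more than a year. The 13 to 14 months separates the earliest possible starts only. The aromatase inhibitor date is a hypothetical example, actual index dates depend on each physician, the required minimum differs by 3 months, and no document gives realised follow-up.

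**The split is by line, not by combination.** This also stands. The 8.7-point figure carries over to Table 1.1 only if line and combination coincide. Eligibility for fulvestrant requires progression on prior endocrine therapy without limiting it to the metastatic setting, so first-line fulvestrant is possible.

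**The study is descriptive and small.** True. With the 7:3 split, about 105 and 45 women, the standard error of the 90%/10% difference at S24 = 70% is √(0.307 × 0.693/105 + 0.237 × 0.763/45) = 7.8 points. The 7.0-point artefact is about the same size, so sampling error does not make it negligible.

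**Conclusion.** The point holds. The visible plan reports a post-baseline outcome as a demographic percentage of all subjects, with no horizon, and splits it by line although follow-up is unequal by design. That percentage cannot answer the 1- and 2-year survival objective, whatever is assumed about death rates.

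The size of the by-line distortion is illustrative: about 5 to 9 points at a 90%/10% mix and about 2.5 to 4 points at 70%/30%, against about 6 to 11 points by combination. These figures rest on equal constant death rates, uniform starts, 2-year survival of 60% to 80% and the stated mixes, none of which is in the documents. It would go too far to say that a later-line disadvantage will be hidden or reversed; that needs a true excess below the factors in the working.

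SAP 4.1 describes all 150 patients as receiving palbociclib with an aromatase inhibitor, whereas the eligibility criteria also admit fulvestrant. Read literally, SAP 4.1 would leave no difference in windows by combination, but the missing horizon would remain. The two passages must be reconciled.

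**What to change.** - Take the deceased row out of SAP 7.2 Demographic Characteristics and out of Tables 1 and 1.1.
- Report deaths with the clinical outcomes (Tables 11 and 11.1), overall and by line: number of deaths, median follow-up, numbers at risk, and Kaplan-Meier survival at 12 and 24 months from palbociclib start, with living women censored at last recorded contact. Protocol 9.7 already foresees Kaplan-Meier with 1- and 2-year rates.
- If the redacted parts of Tables 11 and 11.1 already hold these estimates, move the row there and show it with follow-up time.
- Reconcile SAP 4.1 with the eligibility criteria.

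The cost is an edit to SAP text and shells, which SAP 7.1 says will be final before database lock. Date of death is among the variables in the protocol abstract. Date of last contact is not named in the protocol's variable list, so confirm that the CRF captures it.
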